4.2 Event Monitoring/Survival Follow-up

	Event Monitoring Phase ¹				
	q. 3 months until PD	At PD	After PD q. 6 months	Death	New Primary
Event Monitoring	X	X	X	X	At each occurrence

1. If a patient is still alive 5 years after registration, no further follow-up is required.

¹¹ Repeat imaging needed within 4 weeks of documentation of disease recurrence per RECIST (see [Section 11.0](#)).

¹² Only for Cycle 2 and 3

¹³ Request archived tissue if patient has consented to release of tissue.

¹⁴ Contact [REDACTED] for specifics.

¹⁵ Baseline booklet must be completed after patient has consented and prior to first treatment

5.0 STRATIFICATION FACTORS: None**6.0 REGISTRATION PROCEDURES****6.1 Registration****6.11 Mayo Clinic Sites**

To register a patient, access the Mayo Clinic Cancer Center (MCCC) web page and enter the remote registration/randomization application.

The registration/randomization application is available 24 hours a day, 7 days a week. Back up and/or system support contact information is available on the Web site. If unable to access the Web site, call the MCCC Registration Office at [REDACTED] between the hours of 8 a.m. and 5:00 p.m. Central Time (Monday through Friday).

The instructions for the registration/randomization application are available on the MCCC web page [REDACTED] and detail the process for completing and confirming patient registration. Prior to initiation of protocol treatment, this process must be completed in its entirety and a MCCC subject ID number must be available as noted in the instructions. It is the responsibility of the individual and institution registering the patient to confirm the process has been successfully completed prior to release of the study agent. Patient registration via the registration/randomization application can be confirmed in any of the following ways:

- Contact the MCCC Registration Office [REDACTED]. If the patient was fully registered, the MCCC Registration Office staff can access the information from the centralized database and confirm the registration.
- Refer to "Instructions for Remote Registration" in section "Finding/Displaying Information about A Registered Subject."

6.12 Non-Mayo Clinic sites

To register a patient, fax [REDACTED] a completed eligibility checklist to the Mayo Clinic Cancer Center (MCCC) Registration Office between 8 a.m. and 4:30 p.m. central time Monday through Friday.

6.2 Verification

Prior to accepting the registration, registration/randomization application will verify the following:

- IRB approval of the study
- Patient eligibility
- Existence of a signed consent form
- Existence of a signed authorization for use and disclosure of protected health information

6.3 Documentation of IRB approval

Documentation of IRB approval must be on file in the Registration Office before an investigator may register any patients.

In addition to submitting initial IRB approval documents, ongoing IRB approval documentation must be on file (no less than annually) at the Registration Office (fax: [REDACTED]). If the necessary documentation is not submitted in advance of attempting patient registration, the registration will not be accepted and the patient may not be enrolled in the protocol until the situation is resolved.

When the study has been permanently closed to patient enrollment, submission of annual IRB approvals to the Registration Office is no longer necessary.

6.4 Correlative studies

An optional correlative component is part of this study. There will be an option to select if the patient is to be registered onto this component (see Section 17.2).

- Patient has/has not given permission to use his/her tissue sample for research testing

At the time of registration, the following will be recorded:

- Patient has/has not given permission to store and use his/her sample(s) for future research of cancer at Mayo.
- Patient has/has not given permission to store and use his/her sample(s) for future research to learn, prevent, or treat other health problems.
- Patient has/has not given permission for MCCC to give his/her sample(s) to researchers at other institutions.

6.5 Treatment on protocol

Treatment on this protocol must commence at enrolling institution under the supervision of a medical oncologist or endocrinologist

6.6 Treatment start

Treatment cannot begin prior to registration and must begin ≤ 14 days after registration.

6.7 Pretreatment

Pretreatment tests/procedures (see Section 4.0) must be completed within the guidelines specified on the test schedule.

6.8 Baseline symptoms

All required baseline symptoms (see Section 10.0) must be documented and graded.

6.9a Study drug availability

Study drug is available on site for this patient.

6.9b Booklet availability

Patient questionnaire booklet is available on site for this patient; copies are not acceptable for this submission.

6.9c Consultation with hypertension specialist

A hypertension specialist (endocrinologist, or cardiologist, or nephrologist) at enrolling institution has seen this patient and confirms the patient is a suitable candidate for this study ≤ 14 days prior to registration.

7.0 PROTOCOL TREATMENT

7.1 Treatment Schedule

Treatment will be administered on an outpatient basis. Reported AEs and potential risks are described in Sections 9 and 10. No other investigational or commercial agents or therapies may be administered with the intent to treat the subject's malignancy.

Subjects will receive lenvatinib on an outpatient basis at a dose of 20 mg/day (two 10-mg capsules; dose modification will be accomplished by combining 10-mg and 4-mg capsules as necessary). Subjects are instructed to swallow capsules once a day (preferably in the morning) with or without food with about 1 cup (240 mL) water. Capsules should be swallowed whole; they must not be chewed, broken, or crushed. Treatment continues until progression, excessive toxicity, or patient refuses to continue study medication. Missed and/or withheld doses of lenvatinib (whether intentional or not) are to be reported in the Medication Diary, but not made up.

- Patients will be provided with a Medication Diary for lenvatinib (Appendix II). Patient should bring the diary back at the end of each cycle of treatment.
- Any blood pressure medications patients is already taking or started during the treatment period should be listed in the CRF.

Study drug lenvatinib will be administered at a dose of 20 mg daily by mouth on a 28 day cycle for a maximum of 5 years.

7.11 Treatment medication table

Agent	Dose Level	Route	Day	ReRx
Lenvatinib	20 mg daily	oral	1-28	Q4w

7.2 Criteria for Continuing Treatment

Subjects will be evaluated at each clinic visit during the treatment period to determine if continued treatment is appropriate. If, at any time during treatment the evaluation criteria are not met, lenvatinib will be held or the dose adjusted according to the dose modification criteria stated in [Section 8](#).

To continue therapy, subjects must meet the following criteria:

- Absolute neutrophil count (ANC) $\geq 1,000/\text{mm}^3$ ($1 \times 10^9/\text{L}$),
- Platelet count $\geq 50,000/\text{mm}^3$ ($50 \times 10^9/\text{L}$),
- Blood pressure, if elevated, should be controlled with antihypertensive medication(s),
- Grade ≤ 3 proteinuria or (urinary protein $\leq 3.5 \text{ g}/24 \text{ hrs}$),
- QTc interval $< 500 \text{ msec}$,
- hypokalemia or hyperkalemia \leq Grade 1 or within institutional limits of normal,
- hypocalcemia or hypercalcemia is \leq Grade 2,
- hypomagnesemia or hypermagnesemia is \leq Grade 2; Medical judgment should be exercised in deciding whether an AE of greater than or equal to grade 2 requires dose interruption or modification (see [Section 8.0](#) for Dose Modification guidelines).

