Renal and urinary disorders	Proteinuria Grade ≥ 3		Grade 3, hold lenvatinib until it resolves to Grade 2 or less and resume at one reduced dose level (see Section 8.33) Grade 4, discontinue lenvatinib and enter event monitoring
Skin and subcutaneous tissue disorders	Palmoplantar erythrodysesthesia Grade ≥ 2		Grade 2, hold lenvatinib until it resolves to Grade 1 or less and resume at one reduced dose level Grade 3, discontinue lenvatinib and enter event monitoring

CTCAE System/Organ/Class (SOC)	ADVERSE EVENT	AGENT	ACTION**
Skin and subcutaneous tissue disorders	Maculopapular-rash Grade ≥ 2	lenvatinib	Grade 2, hold lenvatinib until it resolves to Grade 1 or less and resume at one reduced dose level Grade 3, discontinue lenvatinib and enter event monitoring
Vascular disorders	Hypertension Grade ≤ 3		Dose adjust and/or hold lenvatinib and continue to manage per Appendix IV ; consultation with expert recommended Grade 4, discontinue lenvatinib and enter event monitoring
Other non-hematologic adverse events (excluding alopecia)	Grade ≥ 3		Grade 3, hold lenvatinib until AE resolves to Grade 1 or less and resume at one reduced dose level Grade 4, discontinue lenvatinib and enter event monitoring

NOTE: If the patient experiences a significant adverse event requiring a dose reduction at the start of the next cycle, then the dose will remain lowered for that entire subsequent cycle. If that cycle is completed with no further adverse events $>$ Grade 2, then the dose may be increased, at the investigator's discretion, one level at a time, in the following cycles.

NOTE: Adverse events requiring a dose-reduction step for any or all drugs beyond the two dose-reduction steps (levels -1 and -2) will be at the discretion of the treating physician, if the decision is made for the patient to be kept on study. These dose reductions must be clearly recorded in reported clinical data.

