8.33 Management of Proteinuria

If, at any time, a subject has a urine protein/creatinine ratio greater than 1, a 24 hour urine collection must be performed. If a subject develops the nephrotic syndrome, treatment must be discontinued.

Although subjects with $\geq 1+$ proteinuria at entry are ineligible, increases in proteinuria may occur during treatment and should be managed as follows:

Management of Proteinuria	
UPC >1 and <3	Obtain 24-hr urine protein and if <3.4 g, continue at current dose and monitor as clinically indicated
UPC ≥ 3 or 24-h urine protein ≥ 3.5 g	
Step 1: Hold lenvatinib
 
Step 2: Weekly UPC or 24-hr urine protein monitoring until UPC is <3 or 24-hr urine protein is <3 grams
 
Then restart lenvatinib one dose level less
 
Step 3: If UPC >3 or 24-h urine protein ≥ 3 g recurs, repeat Steps 1 and 2
 
Step 4: If UPC ≥ 3 or 24-hr urine protein ≥ 3 recurs and the lenvatinib dose can no longer be reduced, discontinue lenvatinib and remove subject from study

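### The proteinuria limit for continuing lenvatinib in Section 7.2 (Grade 3 or lower) is one grade looser than the hold rule in Section 8.2

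*Combined protocol and SAP*

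**What the plan says.** - **Section 7.2, Criteria for Continuing Treatment.** The list opens with "To continue therapy, subjects must meet the following criteria". The proteinuria bullet begins "Grade ≤ 3 proteinuria or (urinary protein" and closes with an inclusive limit of 3.5 g per 24 hours. If a criterion is not met, the drug is held or the dose adjusted under Section 8. The section ends: "Medical judgment should be exercised in deciding whether an AE of greater than or equal to grade 2 requires dose interruption or modification", with a pointer to Section 8.0.
- **Section 8.2, proteinuria row.** "Grade 3, hold lenvatinib until it resolves to Grade 2 or less and resume at one reduced dose level". At Grade 4 lenvatinib is discontinued.
- **Section 8.33.** With a urine protein/creatinine ratio (UPC) above 1 and below 3, and 24-hour protein below 3.4 g, the instruction is "continue at current dose and monitor as clinically indicated". With UPC of 3 or more, or 24-hour protein of 3.5 g or more, it is "Step 1: Hold lenvatinib".
- **Section 8.0.** The modifications are to be followed strictly for two cycles and are guidelines after that.
- **Section 9.75.** For proteinuria management it names 8.2 and 8.33.

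**The concern.** Section 7.2 sends the reader to Section 8 for a hold or dose change when one of its criteria fails. A patient with Grade 3 proteinuria does not fail, so the route from 7.2 to the 8.2 hold never opens. On the grade wording, 7.2 fails only at Grade 4, where 8.2 has already moved on to discontinuation.

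At stake is consistent dosing safety. Proteinuria is a recognized lenvatinib toxicity: Section 1.233 reports it in 31% of patients in the cited phase 3 thyroid trial, a figure that is not an estimate of Grade 3 events. Treatment can last up to 5 years, so most of a long course falls after cycle 2. In that period the 8.2 hold is guidance, 7.2 leaves events of grade 2 or higher to judgment, and the mandatory wording in 7.2 accepts Grade 3. Two physicians with the same Grade 3 result could act differently and each cite the protocol.

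**Working it through.** The plan gives no figure to reproduce. The check sets the thresholds side by side.

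**Step 1: proteinuria by grade (7.2 and 8.2).**

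| Grade | 7.2 grade criterion | 8.2 action |
|---|---|---|
| 2 or lower | met | none listed |
| 3 | met | hold until Grade 2 or lower, restart one level down |
| 4 | not met | discontinue |

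The sections disagree in the Grade 3 row. Because 7.2 joins its two conditions with *or*, Grade 3 passes whatever the gram value.

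**Step 2: how the other graded limits in 7.2 are set (7.2, 8.31 and 8.2).** If a continuation limit and a hold trigger agree, the highest grade that may continue equals the lowest grade that is held, minus 1.

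| Item | Highest grade continuing (7.2) | Lowest grade held (Section 8) | Held minus continuing |
|---|---|---|---|
| Potassium | 1 | 2 | 2 − 1 = 1 |
| Calcium | 2 | 3 | 3 − 2 = 1 |
| Magnesium | 2 | 3 | 3 − 2 = 1 |
| Proteinuria | 3 | 3 | 3 − 3 = 0 |

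The three electrolyte limits agree with their holds; proteinuria does not. The value that agrees is 3 − 1 = Grade 2, so the stated limit is 3 − 2 = 1 grade too loose. The pattern suggests a slip for Grade 2.

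**Step 3: the gram limit (7.2 and 8.33).** Section 7.2 passes values x ≤ 3.5 g; 8.33 holds at x ≥ 3.5 g. Both apply only at x = 3.5 g. Between 3.4 g and just under 3.5 g, with UPC above 1 and below 3, 8.33 states neither continue nor hold. That is a gap inside 8.33, not a contradiction with 7.2.

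**Step 4: which text governs, and when.** In cycles 1 and 2, Section 8 is strict, so a Grade 3 patient is held whatever 7.2 says. From cycle 3, Section 8 is guidance, while 7.2 has no such time limit. Nothing in the text says which section prevails if they differ.

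**The case against.** The strongest reply is that no two instructions collide. Section 7.2 gives necessary conditions for continuing, not sufficient ones, so a physician who holds at Grade 3 complies with both sections. Section 8 is strict in the first two cycles, 9.75 names 8.2 and 8.33 as the proteinuria guidance, and 7.2 itself points to 8.0. Section 8.33 also requires discontinuation for nephrotic syndrome. The latitude after cycle 2 comes from 8.0, which relaxes the modifications for every toxicity, not from the proteinuria bullet.

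Most of this stands. A reader might infer that the protocol instructs or permits continuing at full dose with Grade 3 proteinuria. The documents do not support that: meeting a necessary condition grants no permission, and Section 8 is very probably the intended rule.

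A reader might also infer a second contradiction because 7.2 has no UPC limit while 8.33 holds at UPC of 3 or more. That is not supported either. Section 7.2 does not set out to list every hold trigger. It also omits phosphate, which 8.31 holds at Grade 3 or higher, and the 60 msec QTc increase in 8.32.

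What the reply does not remove is the stated grade. Where 7.2 does set a limit, that limit should agree with the hold, as the electrolyte limits do.

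**Conclusion.** The proteinuria grade limit in 7.2 is wrong as written, by one CTCAE grade. The gram limit adds only a boundary clash at exactly 3.5 g. The severity is minor: Section 8 still leads to a hold, and the exposure is mainly after cycle 2.

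The conclusion rests on three assumptions:
- The strict-then-guideline rule in 8.0, which names Table 8.1, also covers the adverse-event actions in 8.2 and 8.33.
- The electrolyte pattern shows how 7.2 was meant to work.
- No conversion between CTCAE grade and grams is needed. The documents adopt CTCAE version 4.0 but do not reproduce its proteinuria definitions, and none is used here.

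The number of patients affected cannot be derived from the documents. A reader might infer that uneven holds would bias the response result. The documents give no basis for that. Section 16.11 counts all eligible patients who started lenvatinib, 16.32 keeps patients with incorrect drug administration in the response analysis, and the Simon decision rules do not use this threshold.

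**What to change.** Replace the 7.2 bullet with: *Grade ≤2 proteinuria (hold and restart per Sections 8.2 and 8.33)*. Delete the alternative limit of 3.5 g per 24 hours. If it stayed, joined by *or*, a Grade 3 patient at or below 3.5 g would still pass. Removing it also ends the overlap at exactly 3.5 g and leaves gram and UPC limits to 8.33.

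After the change, the highest continuing grade is 2 and the lowest held grade is 3; the difference is 3 − 2 = 1, as for the electrolytes.

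The cost is a few words in the next amendment, with no change to sample size, visits or tests. There is one real consequence to accept: a hold at Grade 3 becomes mandatory after cycle 2 as well. The 7.2 electrolyte limits already work that way, so this follows the plan's own practice, but the sponsor should adopt it knowingly.

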7.3 Self-administration statement

Patients can be instructed in administration techniques and granted treatment independence with nursing staff approval.

7.4 Return to consenting institution

For this protocol, the patient must return to the consenting institution for evaluation at least every 28 days during treatment.

NOTE: If patient is tolerating treatment well, return visits to Mayo Clinic may be reduced to once every 56-60 days at PI discretion. Required laboratory testing may be done locally and transmitted to Mayo Clinic.

7.5 Treatment by local medical doctor

Treatment by local medical doctor (LMD) is not allowed and patients will be treated only at Mayo clinic.

NOTE: For patients who are tolerating treatment well, safety assessments including labs may be done locally and transmitted to Mayo Clinic at PI discretion.

7.6 Duration of Therapy

In the absence of treatment delays due to adverse event(s) or intolerable toxicity, treatment will continue for a maximum of 5 years or until one of the following criteria applies:

- Disease progression,
- Intercurrent illness that prevents further administration of treatment,
- Unacceptable AE(s),
- Subject decides to withdraw from the study, or
- General or specific changes in the subject's condition render the subject unacceptable for further treatment in the judgment of the investigator.
- Patients who discontinue treatment for any of above reasons will proceed to event monitoring.

7.7 Duration of follow up

- If a patient discontinues treatment due to progression within 5 years of registration, submission of an event monitoring form is required every 6 months thereafter until death or a maximum of 5 years post-registration.
- If a patient discontinues treatment due to reasons other than progression or death within 5 years of registration, submission of an event monitoring form is required every 3 months until progression then every 6 months thereafter until death or a maximum of 5 years post-registration.
- If a patient is deemed ineligible after receiving treatment, all study-related materials including biospecimen data up until the point of confirmation of ineligibility must be submitted. The patient will proceed to event monitoring phase per [Section 4.2](#) of the protocol.
- If a patient does not receive treatment, On-study material and the End of Active Treatment/Cancel Notification Form must be submitted. No further follow-up information is necessary.

8.0 DOSAGE MODIFICATIONS

Strictly follow the modifications in [Table 8.1](#) for the first two cycles, until individual treatment tolerance can be ascertained. Thereafter, these modifications should be regarded as [guidelines](#) to produce mild-to-moderate, but not debilitating, side effects. If multiple adverse events are seen, administer dose based on greatest reduction required for any single adverse event observed. Reductions or increases apply to treatment given in the preceding cycle and are based on adverse events observed since the prior dose.

8.1 Dose Modification Table

If patient is able to tolerate the starting dose of 20 mg daily for the first 2 cycles and if patient shows stable disease (SD) or objective response (OR) by RECIST 1.1 (see Section 11.0), then dose can be escalated to 24 mg daily at the physician's discretion.

Otherwise follow the dose modifications below:

Dose Level	Lenvatinib
+1	24 mg daily
0*	20 mg daily
-1	14 mg daily
-2	10 mg daily

*Dose level 0 refers to the starting dose.

ALERT: ADR reporting may be required for some adverse events (See Section 10.0)

8.2 Dose Modifications Based on Adverse Events

CTCAE System/Organ/Class (SOC)	ADVERSE EVENT	AGENT	ACTION**
Blood and lymphatic system	Anemia* Grade ≥ 3	lenvatinib	Hold treatment until event is \leq Grade 2; reduce one dose level If no recovery to \leq Grade 2 or recurrent Grade 3 or 4, discontinue lenvatinib and enter event monitoring. However, if the subject is benefiting from therapy, contact the PI to discuss course of action.
Cardiac disorders	Acute coronary syndrome Grade ≥ 3		Discontinue lenvatinib and enter event monitoring
Gastrointestinal disorders	Diarrhea Grade ≥ 3		Grade 3, hold lenvatinib until it resolves to Grade 1 or less and resume at one reduced dose level Grade 4, discontinue lenvatinib and enter event monitoring
	Nausea/vomiting Grade ≥ 3 despite antiemetics		Grade 3, hold lenvatinib until it resolves to Grade 1 or less and resume at one reduced dose level Grade 4, discontinue lenvatinib and enter event monitoring

CTCAE System/Organ/Class (SOC)	ADVERSE EVENT	AGENT	ACTION**
Gastrointestinal disorders	Weight loss Grade ≥ 3	lenvatinib	Discontinue lenvatinib and enter event monitoring However, if the subject is benefiting from therapy, contact the PI to discuss course of action
General disorders and administration site conditions	Fatigue Grade ≥ 2		Grade 2, hold lenvatinib until it resolves to Grade 1 or less and resume at one reduced dose level Grade 3, discontinue lenvatinib and enter event monitoring
Endocrine disorders	Hypothyroidism Grade ≥ 3		Grade 3 and 4, hold lenvatinib and replace with levothyroxine until TSH is normalized and resume lenvatinib at same dose
Investigations	Neutrophil count decreased Grade ≥ 3		Hold treatment until event is \leq Grade 2; reduce one dose level If no recovery to \leq Grade 2 or recurrent Grade 3 or 4, discontinue lenvatinib and enter event monitoring However, if the subject is benefiting from therapy, contact the PI to discuss course of action
	Platelet count decreased Grade ≥ 3		Hold treatment until event is \leq Grade 2; reduce one dose level If no recovery to \leq Grade 2 or recurrent Grade 3 or 4, discontinue lenvatinib and enter event monitoring However, if the subject is benefiting from therapy, contact the PI to discuss course of action
Infections and infestations	Any infection Grade ≥ 3		Hold lenvatinib; resume when AE is Grade 1 or less
Metabolism and nutrition disorders	Tumor lysis Grade ≥ 3		Hold lenvatinib until it resolves and resume at one reduced dose level
Renal and urinary disorders	Proteinuria Grade ≥ 3		Grade 3, hold lenvatinib until it resolves to Grade 2 or less and resume at one reduced dose level (see Section 8.33) Grade 4, discontinue lenvatinib and enter event monitoring
Skin and subcutaneous tissue disorders	Palmoplantar erythrodysesthesia Grade ≥ 2		Grade 2, hold lenvatinib until it resolves to Grade 1 or less and resume at one reduced dose level Grade 3, discontinue lenvatinib and enter event monitoring

CTCAE System/Organ/Class (SOC)	ADVERSE EVENT	AGENT	ACTION**
Skin and subcutaneous tissue disorders	Maculopapular-rash Grade ≥ 2	lenvatinib	Grade 2, hold lenvatinib until it resolves to Grade 1 or less and resume at one reduced dose level Grade 3, discontinue lenvatinib and enter event monitoring
Vascular disorders	Hypertension Grade ≤ 3		Dose adjust and/or hold lenvatinib and continue to manage per Appendix IV ; consultation with expert recommended Grade 4, discontinue lenvatinib and enter event monitoring
Other non-hematologic adverse events (excluding alopecia)	Grade ≥ 3		Grade 3, hold lenvatinib until AE resolves to Grade 1 or less and resume at one reduced dose level Grade 4, discontinue lenvatinib and enter event monitoring

NOTE: If the patient experiences a significant adverse event requiring a dose reduction at the start of the next cycle, then the dose will remain lowered for that entire subsequent cycle. If that cycle is completed with no further adverse events $>$ Grade 2, then the dose may be increased, at the investigator's discretion, one level at a time, in the following cycles.

NOTE: Adverse events requiring a dose-reduction step for any or all drugs beyond the two dose-reduction steps (levels -1 and -2) will be at the discretion of the treating physician, if the decision is made for the patient to be kept on study. These dose reductions must be clearly recorded in reported clinical data.

